1.5. Determination of Sample Size

The sample size for Cohorts 1 and 2 are based on safety and PK considerations.

The sample size for Cohort 3 is based on a 2-sample t-test assuming an improvement in DAS28-CRP change from baseline (CFB) for the KPL-404 being 1.2 points better than placebo (KPL-404 group CFB improvement = 2.2 points, placebo group CFB improvement = 1.0 point, standard deviation = 1.3). With 21 subjects in each of the 3 treatment groups (KPL-404 5 mg/kg qwk, KPL-404 5 mg/kg q2wk, and placebo) having completed 12 weeks of DAS28-CRP assessments, there is 83% power for the treatment comparison of active vs. placebo with 2-sided 0.05 type 1 error. In order to maintain this level of power after accounting for an anticipated discontinuation rate of 16%, up to 25 subjects per treatment group and up to a total of 75 subjects would need to be enrolled in Cohort 3.

The sample size for Cohort 4 is based on a 2-sample t-test assuming an improvement in DAS28-CRP change from baseline for the KPL-404 being 1.3 points better than placebo (improvement for placebo = 1.0 point, standard deviation = 1.3). Enrollment of 22 subjects into the KPL-404 arm and 14 subjects into the placebo arm (i.e., 3:2 randomization ratio) allows 80% power for the treatment comparison with 2-sided 0.05 type 1 error if all subjects complete 12 weeks of DAS28-CRP assessments. In order to account for an anticipated discontinuation rate of 10%, approximately 24 subjects (KPL-404) and 16 subjects (placebo) for a total of approximately 40 subjects are required to enroll under Cohort 4.

2. STUDY ANALYSIS POPULATIONS

2.1. Modified Intent-to-Treat (mITT) Population

All randomized subjects who receive at least one dose of study drug and have a baseline assessment and at least one post-baseline assessment for primary efficacy endpoint will be included in the mITT population. Efficacy analyses will be based on the mITT population.

2.2. Per Protocol (PP) Population

All mITT subjects who have no important protocol deviations that may potentially bias efficacy analyses of the study. These deviations will be pre-specified prior to study unblinding/database lock.

2.3. Safety Population

All randomized subjects who receive at least one dose of study drug will be included in the safety population. Safety analyses will be based on the safety population.

3. GENERAL STATISTICAL CONSIDERATIONS

All analyses and summaries will be produced using SAS® version 9.4 (or higher).

For inferential statistical analyses, each treatment group of KPL-404 will be compared to placebo. Unless otherwise specified, all tests will be at two-tailed using pre-specified level of significance 0.05.

Descriptive statistics (n, mean, standard deviation [SD], median, Q1, Q3, minimum, and maximum) will be presented for continuous variables. For continuous efficacy endpoints, least square (LS) mean, LS mean difference, standard error (SE), and 95% confidence interval (CI) will be calculated.

For categorical variables (including binary variables), counts and percentages will be presented. For binary efficacy endpoints, 95% CI for difference in proportion and p-values will be presented.

Time to event data will be analyzed using the Kaplan-Meier (KM) method, which will include the estimated median with 95% confidence interval (CI) and the 25th and 75th percentiles.

Subject listings for all randomized subjects will be provided for all efficacy and safety data. In general, the subject listings will be sorted by cohort, treatment group, subject number and assessment date (and time, if applicable).

For Cohorts 1 and 2, pooled data will be analyzed by treatment group. Data from Cohorts 3 and 4 will be analyzed separately.

3.1. Baseline Value and Change from Baseline

The baseline value of efficacy parameters is defined as the last non-missing value before randomization and prior to the first dose of study medication otherwise specified.

For safety endpoints, baseline is defined as the last non-missing value obtained prior to the first dose unless otherwise specified.

Change from baseline, where applicable, will be calculated at each visit over time as the post-baseline evaluation minus the baseline evaluation.

3.2. Study Day

For efficacy endpoints analyses, study day is defined as the number of days from randomization date to the event/visit date. It is calculated as follows:

• If the event date falls on or after randomization date.

Study day = Event or visit date - randomization date + 1

• If the event date falls before randomization date.

Study day = Event or visit date – randomization date

For safety endpoints analyses, treatment day is defined as the number of days from first dose date to the event/visit date. It is calculated as follows:

- If the event date falls on or after first dose date,
 - Treatment day = Event or visit date first dose date + 1
- If the event date falls before first dose date,
 - Treatment day = Event or visit date first dose date

3.3. Analysis Visits

Efficacy assessments

For the efficacy assessment, the reference date for the derivation of relative days of events or findings will be the randomization day. If a subject receives treatment dose prior to the randomization by mistake, the reference date of efficacy assessment will be the date of the first treatment dose administration for that subject.

For efficacy variables, all available values of scheduled measurements will be assigned to the appropriate visit window according to Table 2. In the event of multiple measurements of the same test in the same window, the one closest to the targeted visit date will be used for the by-visit summary. If they are at the same number of days away from the target day, the latest one will be used. Randomization day is used as the reference day (Day 1).

Table 2: Time window for efficacy variables

	,	Time	e windows for
Visit	Target Day	TJC68/SJC66	ACR20/50/70, DAS28-CRP, HAQ-DI,
Screening (Days -28 to -1)	<1	≤-1	
Baseline (Week 0)	1	≤1	≤1
Week 2	15	2-22	2-22
Week 4	29	23-43	23-43
Week 8	57	44-71	44-71
Week 12	85	72-92	72-92
Week 14	99	93-106	93-106
Week 16	113	107-127	107-127
Week 20	141	128-155	128-155
Week 24	169	>155	>155

Safety assessment

For the safety assessment, the reference date for the derivation of relative days of events or findings will be the date of first IP administration. Selected safety variables will be summarized by the analysis window defined in Table 3 for the by visit descriptive analysis. All available values will be assigned to the appropriate visit window. In the event of multiple measurements of the same test in the same window, the one closest to the targeted visit date will be used for the by-visit summary. If they are at the same number of days away from the target day, the latest one will be used. First IP day is used as the reference day (Day 1).

Table 3: Time window for safety endpoints

					Tiı	me window	s for		
Visit	Target Day	Vital signs	CRP,	Chemistry, Hematology, Coag. panel	Urinaly sis	Urine pregna ncy test	Height *, Weight	Physica l examin ation	EC G
Screening (Days -28 to -1)	<1	≤-1	≤-1	≤-1	≤-1	≤-1	≤-1	≤-1	≤- 1
Baseline (Week 0)	1	<1-	<1-	<1-	<1-	<1-	≤1	≤1	
Week 2	15	2-22	2-22	2-22	2-22				
Week 4	29	23-43	23-43	23-43	23-43	243			
Week 8	57	44-71	44-71	44-71	44-71	44-71			
Week 12	85	>71	72-92	>71	>71	72-99	>1	>1	>1
Week 14	99		93-106						
Week 16	113		107-127			100-127			
Week 20	141		128-155			128-155			
Week 24	169		>155			>155			

^{*} Height is collected at Screening visit only.

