11.7. Analysis of Safety

Descriptive statistics and changes from baseline, as applicable, will be calculated for safety parameters. No inferential statistical analyses are planned. The details regarding analyses will be provided in the SAP. Additional exploratory and post hoc analyses of the data may be conducted as deemed appropriate.

Analysis of TEAEs, defined as AEs that start or increase in severity after the first dose of study drug during treatment period, will be coded to system organ class and preferred term using the latest version of MedDRA. Analysis of post-treatment AEs, defined as any AEs that occur during the off-treatment period, will also be summarized in a similar manner.

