 - If serum pregnancy test result is borderline, a repeat test is necessary to confirm eligibility. If still borderline ≥ 3 days later, this will be considered documentation of continued lack of a positive result, and the subject can be enrolled into the study.
- Minimum 8-hour fast. If a subject is unable to fast when necessary, the nonfasting status will be recorded.
- A urine dipstick macroscopic urinalysis will be completed by the central laboratory at all required visits. L
- M If urine pregnancy test is positive, withhold dosing and perform a serum pregnancy test. Pregnant subjects must permanently discontinue IP. N All blood draws (including PK) must be done pre-dose at applicable visits.
 - All blood draws (including PK) must be done pre-dose at applicable visits.

{Confidential}

KPL-404 Study KPL-404-C211

Schedule of Activities – Cohort 4

Study Period	Screening Period			Treatment Period	nt Period				Safety Follo	Safety Follow up Period	
Week	Screening	Baseline	Wk 1	Wk 2	Wk 4	Wk 8	Wk 12/ EOT ^a	Wk 14	Wk 16	Wk 20	Wk 24/EOS
Day	-28 to -1	П	∞	15	29	57	85	66	113	141	169
Visit Window			± 2 days	± 2 days	± 2 days	± 2 days	± 2 days	± 4 days	± 4 days	± 4 days	± 4 days
Informed consent	X										
Demographics	X										
Eligibility criteria	X	X									
Medical/surgica I history ^b	X	X									
Randomization		X									
Safety assessments											
Adverse events ^c	X	X	X	X	X	X	X	X	X	X	X
Chest x-ray ^d	X										
12-lead ECG	X^{q}						X				
Physical examination ^e	Х	X					X				
Vital signs ^f	X	X		X	X	X	X				
Height (screening only) and weight	X	X					X				
Prior/concomita nt medications and therapies	X	X	×	X	X	X	X	X	X	X	X

KPL-404 Study KPL-404-C211

Study Period	Screening Period			Treatme	Treatment Period				Safety Follo	Safety Follow up Period	
Week	Screening	Baseline	Wk 1	Wk 2	Wk 4	Wk 8	Wk 12/ EOT ^a	Wk 14	Wk 16	Wk 20	Wk 24/EOS
Day	-28 to -1	-	œ	15	29	57	85	66	113	141	169
Visit Window			± 2 days	± 2 days	± 2 days	± 2 days	± 2 days	± 4 days	± 4 days	± 4 days	± 4 days
RA assessments											
TJC68/SJC66	X	X		X	X	X	X	X	X	X	X
ACR20/50/70		×		X	X	X	X	X	×	X	X
DAS28-CRP		X		X	X	X	X	X	X	X	X
HAQ-DI ^g		X		X	X	X	X	X	X	X	Х
Blood collection":											
QuantiFERON test	X										
HBV/HCV	X										
HIV (local laboratory) ^h	Х										
Serum β-hCG for WOCBPi	X										X
Central hs-CRP	X	X		X	X	X	X	X	X	X	X
Blood chemistry ^j	×	×		×	×	×	X				

Study Period	Screening Period			Treatment Period	rt Period				Safety Follow up Period	w up Period	2 2)

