Week	Screening	Baseline	Wk 1	Wk 2	Wk 4	Wk 8	Wk 12/ EOTª	Wk 14	Wk 16	Wk 20	Wk 24/EOS
Day	-28 to -1	1	æ	15	29	57	88	66	113	141	169
Visit Window			±2 days	± 2 days	±2 days	±2 days	± 2 days	± 4 days	± 4 days	± 4 days	± 4 days
Hematology (CBC) with differential	x	X		Х	х	Х	X				
Coagulation panel	X	X		X	X	X	X				
							35 P3	-			
Pharmacokineti c samples (serum)		x	х	X	х	Х	x	х	x	х	x
Urine collection:			6. 7.		AT.						
Urinalysis ¹	X	X		X	X	X	X				
Urine β-hCG for WOCBP (local) ^m		x			х	Х	х		x	х	x
Urine drug screen	X										
$\begin{array}{c} \mathbf{P} \\ \mathbf{administration}^n \end{array}$		х			X	X					
AE = adverse event; chorionic gonadotropin; CBC = complete blood count; chorionic gonadotropin; CBC = complete blood count; chorionic gonadotropin; ECG = electrocardiogram; EOS = end of study; EOT = end of treatment; HAQ-DI = Health Assessment Questionnaire Disability Index; HBV = hepatitis B virus; HCV = hepatitis C virus; HIV = human immunodeficiency virus, hs-CRP = high-sensitivity C-reactive protein; IP = investigational product;	ent; otropin; CBC lectrocardiog	= complete b ram; EOS = e rus; HIV = hu	lood count; nd of study; man immuno	; ACR EOT = end of deficiency vii	reatment; H	College of R IAQ-DI = He = high-sensit	; ACR = American College of Rheumatology; DAS28-CRP = disease activity score of 28 joints using C-reactive end of treatment; HAQ-DI = Health Assessment Questionnaire Disability Index; HBV = hepatitis ncy virus, hs-CRP = high-sensitivity C-reactive protein; IP = investigational product;	: = disease activ ent Questiom ve protein; IP	vity score of 2 naire Disabilii = investigati	; β-hCG = beta-human 28 joints using C-reactive ty Index; HBV = hepatiti onal product;	veta-human g C-reactive V = hepatitis

Version 6.0: 28 Jun 2023

SIC = swollen joint count; TJC = tender joint count; Wk = week; WOCBP = women of childbearing potential. ; SAE = serious adverse event; RA = rheumatoid arthritis;

- approximately 2 weeks after discontinuation, and the subject should be encouraged to complete the remaining visits at Weeks 2, 4, 6, 8, 10, 12, 14, 16, 20 and A If a subject prematurely discontinues prior to the completion of the treatment period (Week 12), the procedures for the EOT visit should be conducted within

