4.7. Safety Analyses

All safety analyses will be conducted by treatment group in the Safety population for clinical and laboratory parameters, vital sign, and for adverse events (AEs). Adverse events will be coded using MedDRA of the version at database lock. Laboratory parameters, vital signs, and ECG data will be summarized as descriptive statistics by treatment, visit, and study period.

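### SAP Table 3 leaves the Week 12 window for labs, vital signs and ECG open to study end, so an unscheduled off-treatment value can be reported as Week 12 for a subject without a Week 12 test

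*SAP*

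**What the plan says.** - **Schedule (Protocol Appendix 1, repeated in SAP 8.1).** In all cohorts, the rows for chemistry, hematology, "Coagulation panel", urinalysis, vital signs and ECG have their last mark at Week 12/EOT. The exceptions are "Central hs-CRP" and the pregnancy tests, which continue to Week 24.
- **Which values enter a window (SAP 3.3).** For efficacy, "all available values of scheduled measurements will be assigned". For safety, "All available values will be assigned to the appropriate visit window".
- **The Week 12 safety windows (SAP Table 3).** The row reads "Week 12 85 >71 72-92 >71 >71 72-99 >1 >1 >1". After the target day, the columns are vital signs; CRP; chemistry, hematology and coagulation; urinalysis; urine pregnancy test; weight; physical examination; ECG. CRP and urine pregnancy are closed and have later windows. The others have no upper limit and no later window.
- **Several values in one window (SAP 3.3).** "the one closest to the targeted visit date will be used for the by-visit summary"; a tie goes to the latest.
- **Summaries.** SAP 4.7: "Laboratory parameters, vital signs, and ECG data will be summarized as descriptive statistics by treatment, visit, and study period". SAP 4.7.3 averages repeated vital signs at a visit. SAP 4.7.4 uses the last repeated ECG, or the last abnormal one if interpretations differ. The SAP 4.7.2 shift table uses the lowest or highest post-baseline value, with no end date.
- **Adverse events (Protocol 11.7).** "Analysis of post-treatment AEs, defined as any AEs that occur during the off-treatment period, will also be summarized in a similar manner".

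**The concern.** After Week 12, any further value of these tests is unscheduled. It is likely to have been taken for a clinical reason, from a subject who is off treatment. The safety rule admits such values, and the open window gives them only one label, Week 12. SAP 3.4 does not impute missing safety data, yet here the window itself can fill a missing Week 12 value with one taken weeks later.

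At stake is the reading of the last on-treatment safety summary. A follow-up summary by study period would consist only of selected, unscheduled tests. A fall in lab, vital-sign or ECG adverse events after treatment could also be read as recovery when scheduled testing has simply stopped.

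**Working it through.** **1. Reproduce Table 3.** Each bound is the midpoint between consecutive scheduled target days, with the last scheduled visit left open.
- Week 12 lower bound: (57 + 85)/2 = 71, so the window starts at Day 72.
- CRP upper bound: (85 + 99)/2 = 92, giving 72-92.
- Urine pregnancy upper bound: (85 + 113)/2 = 99, giving 72-99.
- Labs, urinalysis and vital signs have no later visit, hence >71. ECG has one post-baseline visit, hence >1.

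The legible windows all reproduce, so the open end is the table's convention and not a slip.

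**2. Window length.** Week 24 is Day 169 with a 4-day allowance, so the last day is 173.
- Labs, urinalysis and vital signs: 173 - 72 + 1 = 102 days.
- CRP: 92 - 72 + 1 = 21 days.
- ECG: 173 - 2 + 1 = 172 days.

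**3. Subject tested at Week 12.** A later value on Day y replaces a value on Day x only if |y - 85| ≤ |x - 85|.
- x = 85 or 87: no later day qualifies.
- x = 83: only Days 84-87 qualify.
- The earliest follow-up visit is Day 99 - 4 = 95, at distance 10, and never qualifies.

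**4. Subject with no lab or vital sign on Days 72-92.** An early-EOT lab from before Day 72 falls in an earlier window, so Week 12 is empty. An unscheduled value on, say, Day 140 is then the only one in the window and is reported as Week 12, although it is 140 - 85 = 55 days from target.

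**5. ECG after early discontinuation.** The early-EOT ECG is itself inside the >1 window. From step 3, with x < 85, it is displaced by any later ECG up to Day y = 170 - x.

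| Early-EOT ECG | Displaced by a later ECG up to |
|---|---|
| Day 30 | Day 140 |
| Day 45 | Day 125 |
| Day 60 | Day 110 |

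Weight has the same window and the same exposure.

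**6. Repeat rules.** If the averaging rule (4.7.3) or the last-abnormal rule (4.7.4) is applied across the analysis window, a follow-up value could alter Week 12 even for a subject tested on Day 85. That would conflict with the closest-value rule in 3.3. The SAP does not say which governs.

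**7. Rough exposure (SAP 1.5).** 0.16 × 75 = 12 in Cohort 3 and 0.10 × 40 = 4 in Cohort 4. No rate is given for Cohorts 1 and 2. These are planned discontinuations. Substitution of a lab or vital sign also needs an absent Week 12 value and a later unscheduled test. A completer who misses Week 12 is exposed in the same way.

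**8. Follow-up.** The number of these tests scheduled at Weeks 14, 16, 20 and 24 is zero in every cohort.

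**9. End of treatment (SAP 4.5).** On nominal dosing days, treatment ends on 71 + 13, 78 + 6 or 57 + 27, each Day 84. That is one day before the Week 12 visit, which matters for wording the fix.

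**The case against.** The strongest reply is that the SAP already limits the problem. The closest-value rule protects lab results for anyone tested at Week 12. Leaving the last window open is how Table 3 treats every test, and >1 for ECG sensibly captures early-EOT tracings. Discontinued subjects are asked to complete EOT procedures and later visits (Protocol 7.3), and the Cohort 3 and 4 schedule footnotes list Week 12 among those visits. By-subject listings would show the date of a late value. All of this stands, and it makes the point small. It does not remove the cases in steps 4 and 5, where the written rule yields a mislabelled value.

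Three stronger readings are tempting, but the documents do not support them:
- *Follow-up tests in general become Week 12 values.* Step 3 rules this out for labs from subjects tested at Week 12.
- *About 4 of 25 subjects per Cohort 3 arm will have a substituted value.* That is 16% planned discontinuation, so for early discontinuers it is a ceiling. The documents give neither missed-visit nor unscheduled-test rates.
- *The adverse event comparison is biased, or lab-detected events are moved to the post-treatment period by construction.* Arms within a cohort share one schedule, so reduced detection affects the on- versus off-treatment reading, not mainly active versus placebo. Symptoms and unscheduled tests can still reveal events. Those found at Weeks 2, 4 or 8 in subjects still on treatment are on-treatment, and no inferential safety analysis is planned (Protocol 11.7).

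**Conclusion.** The concern holds in a limited form and is minor. As written, the SAP can report an unscheduled, off-treatment lab or vital sign from Day 93 onward as Week 12 when a subject has no value on Days 72-92. It can also replace an early-EOT ECG or weight with a later unscheduled one. Summaries of these tests for the follow-up period would rest on unscheduled testing alone.

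The number affected cannot be derived. About 12 of 75 and 4 of 40 are rough planning figures for exposure, not estimates of substituted values. The conclusion assumes that unscheduled tests are entered in the database and windowed as Section 3.3 states; Protocol 7.3 provides for unscheduled visits. The tables are descriptive and the arms share a schedule, so no efficacy or between-arm safety conclusion depends on this. The change is a cheap improvement.

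**What to change.** Amend the SAP before database lock:
1. In Table 3, change >71 to 72-92 for vital signs, chemistry, hematology, coagulation and urinalysis, the bound already used for CRP.
2. Limit by-visit safety summaries to scheduled and early-EOT tests, including ECG and weight.
3. Report values after Day 92 in a separate unscheduled follow-up table or listing.
4. State that the repeat rules in 4.7.3 and 4.7.4 apply within a single visit, not across the analysis window. Present the worst-value shift table for the treatment period, as the neutropenia summary in 4.7.2 already is. State that this period includes the Week 12/EOT sample, because the 4.5 formula ends on Day 84 and would otherwise exclude a Day 85 test.
5. Footnote the post-treatment adverse event table: no safety labs, vital signs or ECGs were scheduled after Week 12 (hs-CRP and pregnancy tests apart), so fewer such events in follow-up is not evidence of recovery.

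The cost is wording, one footnote and minor programming, with no added test or visit. The downside is a few more missing Week 12 values, including any Week 12 visit held after Day 92.

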3.4. Missing Data Handling

Missing data handling for efficacy endpoints are specified in Section 4.6. No imputation will be performed for missing data for safety endpoints, unless otherwise specified. Incomplete AE start/end dates and incomplete medication start/end dates will be discussed in Section 8.2.

3.5. Analysis Timing

For Cohorts 1 and 2, the primary efficacy analysis will be performed after the last subject has completed the 12-week treatment period and data have been cleaned. While the follow-up period is ongoing, the study team with daily activities, investigational sites, or enrolled subjects will be kept blinded to the analysis results. The final analysis will be conducted after all subjects have completed the 24-week study and data have been cleaned for these two cohorts. The IP treatment for each subject in these two cohorts will still be kept blinded to the study team with daily activities, investigational sites, or enrolled subjects until the final database lock.

Please note that the analyses of Cohorts 1 and 2 at either Week 12 or at Week 24 should not be considered as an interim analysis, as Cohorts 1 and 2 are independent from Cohorts 3 and 4, which are the proof-of-concept portion of the study. In our primary efficacy analyses for Cohorts 3 and 4, data from Cohorts 1 and 2 will not be pooled with data from Cohorts 3 or 4. Hence there is no impact for Cohort 3 or Cohort 4 conduct and analyses.

For Cohort 3 and subsequently for Cohort 4, the primary analysis during the treatment period will be performed when all randomized subjects in a particular cohort have completed their 12-week treatment period and data have been cleaned. While the follow-up period is ongoing, the study team with daily activities, investigational sites, or enrolled subjects will be kept blinded to the individual results and IP treatment for each subject until the final database lock.

After all randomized subjects in Cohorts 3 and subsequently Cohort 4 have completed their 24-week study to include the post-treatment follow-up information and data have been cleaned, the database for each cohort will be locked sequentially. The final analysis for each cohort will be based on the individual final database lock.

